9.4.9 Pharmacokinetic/Pharmacodynamic Correlations

No PK/PD correlations are planned for this study.

9.4.10 Immunogenicity

Immunogenicity results, including overall ADA results (Screening, confirmatory, and titers, as appropriate), neutralizing ADA results, and the time course of antibodies (defined as the time to first observation of a positive ADA response) will be listed. The number and percentage of subjects testing positive for ADAs or neutralizing antibodies will be summarized by dose treatment group over time. If applicable, the time course of antibodies may be summarized by treatment group using appropriate descriptive statistics.

9.5 Subgroup Analysis

All subgroup analyses will be exploratory (post hoc) in nature. The details of these analyses will be described in the SAP and provided prior to the database lock. No specific subgroup analysis will be described in detail in the protocol.

9.6 Safety Monitoring Committees

A DSMB and CVAC will oversee the study from a safety and CV monitoring perspective, as described in Section 7.4.4.

9.7 Interim Analysis

For any interim data cuts or analyses which occur, the details will be specified in the SAP.

10. ETHICS

10.1 Institutional Review Board/Independent Ethics Committee

An IRB/IEC should approve the final protocol, including the final version of the ICFs and any other written information and/or materials to be provided to the subjects. The Investigator will provide R-Pharm International or R-Pharm International's designee with documentation of IRB/IEC approval of the protocol and the ICFs before the study may begin at the study site(s). The Investigator should submit the written approval to R-Pharm International or its designee before enrollment of any subject into the study.

R-Pharm International or its designee should approve any modifications to the ICF that are needed to meet local requirements.

The Investigator will supply documentation to R-Pharm International or R-Pharm International's designee of required IRB/IEC's annual renewal of the protocol, and any approvals of revisions to the ICF or amendments to the protocol.

The Investigator will report promptly to the IRB/IEC, any new information that may adversely affect the safety of subjects or the conduct of the study. Similarly, the Investigator will submit written summaries of the study status to the IRB/IEC annually, or more frequently if requested by the IRB/IEC. Upon completion of the study, the Investigator will provide the ethics committee with a brief report of the outcome of the study, if required.

R-Pharm International or its designee will handle the distribution of any of these documents to the national regulatory authorities.

R-Pharm International or its designee will provide Regulatory Authorities, IRBs/IECs, and Investigators with safety updates/reports according to local requirements, including SUSARs, where relevant.

Each Investigator is responsible for providing the IRB/IEC with reports of any serious and unexpected adverse drug reactions from any other study conducted with the study treatment. R-Pharm International or its designee will provide this information to the Investigator so that he/she can meet these reporting requirements.

10.2 Ethical Conduct of the Study

The GCP is an international ethical and scientific quality standard for designing, conducting, recording, and reporting studies that involve the participation of human subjects. The study will be conducted in compliance with GCP and the applicable national regulations so as to

assure that the rights, safety, and well-being of the participating study subjects are protected consistent with the ethical principles that have their origin in the Declaration of Helsinki.

10.3 Subject Information and Informed Consent

The ICFs (i.e., ICF for subjects and a separate ICF for caregivers [if applicable]) will be used to explain the risks and benefits of study participation to the subject in simple terms before the subject will be entered into the study. The ICFs contains a statement that the consent is freely given, that the subject is aware of the risks and benefits of entering the study, and that the subject is free to withdraw from the study at any time. Written consent must be given by the subject and/or legal representative after the receipt of detailed information on the study.

All ICFs must be available in the local and vernacular languages required at the study site and include subject information sheets/brochures that outline the study procedures. All ICFs must be signed and dated by the subject or a legally acceptable representative.

For subjects who are unable to read and write, the subject information sheet and ICF should be read to the subject in his/her native language in the presence of an impartial witness who is literate and not affiliated with the study. The subject having understood the information given to him/her in the presence of an impartial witness will thumbprint the ICF and the same will be countersigned by the impartial witness. If the subject or legally acceptable representative cannot read then an impartial witness will witness and attest the entire consent process and will be required to sign the consent form. Confirmation of a subject's informed consent must also be documented in the subject's medical record prior to any testing under this protocol, including Screening tests and assessments.

The Investigator is responsible for ensuring that informed consent is obtained from each subject or legal representative and for obtaining the appropriate signatures and dates on the ICF prior to the performance of any protocol procedures and prior to the administration of study treatment. The Investigator will provide each subject with a copy of the signed and dated consent form while the originals will be retained in the Investigator's records.

10.4 Subject Data Protection

The ICF will incorporate or, in some cases, be accompanied by a separate document incorporating wording that complies with relevant data protection and privacy legislation. R-Pharm International or R-Pharm International's designee will not provide individual results to subjects, any insurance company, any employer, their family members, general physician, or any other third party, unless required to do so by law.

Information about study subjects will be kept confidential and managed according to the regulatory requirements.

11.2 Study and Study Site Closure

Upon completion of the study, the monitor will conduct the following activities in conjunction with the Investigator or study site staff, as appropriate, including the following:

- Return of all study data to R-Pharm International
- Resolution of data queries
- Accountability, reconciliation, and arrangements for unused study treatments
- Review of study site, study records for completeness
- Review requirements for record retention and audit responsibilities

11.3 Study Discontinuation

The study may be discontinued at any time by the IRB/IEC, R-Pharm International, or regulatory agencies as part of their duties to ensure that research subjects are protected.

R-Pharm International reserves the right to temporarily suspend or prematurely discontinue this study either at a single study site or at all study sites at any time for reasons including safety or ethical issues or severe noncompliance. If R-Pharm International determines such action is needed, R-Pharm International will discuss this with the Investigator (including the reasons for taking such action) at that time. When feasible, R-Pharm International will provide advance notification to the Investigator of the impending action prior to its taking effect.

R-Pharm International will promptly inform all other Investigators and/or institutions conducting the study if the study is suspended or terminated for safety reasons, and will also

inform the regulatory authorities of the suspension or termination of the study and the reason(s) for the action. If required by applicable regulations, the Investigator must inform the IRB/IEC promptly and provide the reason for the suspension or termination.

If the study is prematurely discontinued, all study data must be returned to R-Pharm International or its designee. In addition, arrangements will be made for return of all unused study treatments in accordance with R-Pharm International's applicable procedures for the study.

Financial compensation to Investigators and/or institutions will be in accordance with the agreement established between the Investigator and R-Pharm International.

11.4 Data Handling and Record Keeping

Information about study subjects will be kept confidential and managed according to the regulatory requirements. It is the Investigator's responsibility to maintain essential study documents (protocol and protocol amendments, completed eCRFs, signed ICFs, relevant correspondence, and all other supporting documentation). The study site should plan on retaining such documents for approximately 15 years after study completion. The study site should retain such documents until at least 2 years after the last approval of a marketing application in an ICH region and until there are no pending or contemplated marketing applications in an ICH region or at least 2 years after the formal discontinuation of clinical development of the study treatment. These documents should be retained for a longer period if required by the applicable regulatory requirements or the hospital, institution, or private practice in which the study is being conducted.

Subject identification codes (subject names and corresponding study numbers) will be retained for this same period of time. These documents may be transferred to another responsible party, acceptable to R-Pharm International, who agrees to abide by the retention policies. Written notification of transfer must be submitted to R-Pharm International. The Investigator must contact R-Pharm International prior to disposing of any study records.

No records should be disposed of without the written approval of R-Pharm International.

11.5 Direct Access to Source Data/Documents

The Investigator will prepare and maintain adequate and accurate source documents to record all observations and other pertinent data for each subject randomized into the study.

Source data is all information, original records of clinical findings, observations, or other activities in a clinical study necessary for the complete reconstruction and evaluation of the study. Source data are contained in source documents. Examples of these source documents

and data records include: hospital records, clinical and office charts, laboratory notes, memoranda, subject's evaluation checklists, pharmacy dispensing records, recorded data from automated instruments, copies or transcriptions certified after verification as being accurate and complete, microfiches, photographic negatives, microfilm or magnetic media, radiographs, subject's records, and records kept at the pharmacy, at the laboratories, and at medico-technical departments involved in the clinical study.

The Investigator will allow the authorized R-Pharm International's designee and authorized regulatory authorities and IRBs/IECs to have direct access to all documents pertaining to the study, including individual subject medical records, as appropriate.

11.6 Investigator Information

11.6.1 Investigator Obligations

The Investigator is responsible for ensuring that all study site staff, including sub-Investigators, adhere to all applicable regulations and guidelines, including local laws and regulations, regarding clinical studies both during and after study completion.

The Investigator is responsible for informing the IRB/IEC of the progress of the study, for obtaining annual IRB/IEC renewal, and informing the IRB/IEC of completion of the study and will provide the IRB/IEC with a summary of the results of the study.

The study will be conducted in compliance with the protocol, GCP, and the applicable regulatory requirements of European Commission Directive (2001/20/EC Apr 2001) and/or European Commission Directive (2005/28/EC Apr 2005) and/or the US Food and Drug Administration GCP Regulations: Code of Federal Regulations Title 21, parts 11, 50, 54, 56, and 312, and/or other applicable local or regional regulations.

The Investigator agrees to conduct the clinical study in compliance with this protocol after the approval of the protocol by the IRB/IEC in compliance with local regulatory requirements. The Investigator and R-Pharm International will sign the protocol to confirm this agreement.

The Investigator is encouraged to discuss the withdrawal of a subject, from either treatment or study, with R-Pharm International or R-Pharm International's designee, in advance, whenever is possible. In addition, any case when a subject deviated from the dosing schedule or missed any scheduled treatment should be reported to R-Pharm International and/or R-Pharm International's designee promptly, for making decision whether the study participation should be continued.

Medical Monitor should be contacted before restarting the study treatment after any interruption of study treatment. Medical Monitor should be contacted in case of potential hepatotoxicity events that fulfill any of the criteria of seriousness to investigate all potential causes of liver toxicity (see Section 7.4.3.4).

11.6.2 Protocol Signatures

After reading the protocol, each Investigator will sign the protocol signature page and send a copy of the signed page to R-Pharm International or its designee. By signing the protocol, the Investigator confirms in writing that he/she has read, understands, and will strictly adhere to the study protocol and will conduct the study in accordance with the ICH Tripartite Guidelines for GCP and applicable regulatory requirements. The study will not be able to start at any study site where the Investigator has not signed the protocol.

11.6.3 Publication Policy

R-Pharm International shall retain the title and the right to publish all documentation, records, raw data, specimens or other work product generated pertaining to the study ("data") conducted by the study site (study site includes the Investigator and the institution) as defined in the applicable protocol or study plan or study agreement. The study site shall maintain confidentiality and not disclose or divulge such "data" to any third party. However, the study site may seek permission to publish such "data" for limited purpose and such "data" may be published by the study site only upon receipt of prior written approval from R-Pharm International.

11.7 Financing and Insurance

R-Pharm International is the Sponsor of the study. R-Pharm International will provide insurance in accordance with local guidelines and requirements as a minimum for the subjects participating in this study. The terms of the insurance will be kept in the study files.

R-Pharm International has obtained liability insurance, which covers this study as required by local law and/or national regulations and/or ICH guidelines, whichever is applicable. The terms of the insurance will be kept in the study files.

13. APPENDICES

13.1 Appendix 1: Methotrexate Dose Reduction Guidelines

ALT and/or AST	Total Bilirubin	Repeat Laboratory	MTX	Study Treatment
1× to ≤2× ULN	NA	No need	No change	No change
>2× to ≤3× ULN	NA	Within 1 week	No change or can consider reduction in dose	No change
If repeat $>2 \times$ to $\leq 3 \times$ ULN	NA	Within 1 week	Reduce dosage and follow LFTs	No change
>3× to <8× ULN (without the appearance of fatigue, nausea, vomiting, right upper quadrant pain or tenderness, fever, rash, and/or eosinophilia [>5%])	≤2× ULN	Within 72 hours of initial finding, and then at least weekly after last finding until resolution, stabilization, or return to baseline values	en at least weekly after last g until resolution, zation, or return to baseline Hold MTX until LFTs normalize or return to baseline and consider	
If repeat >3× to <8× ULN (without the appearance of fatigue, nausea, vomiting, right upper quadrant pain or tenderness, fever, rash, and/or eosinophilia [>5%])	≤2× ULN	Within 72 hours of initial finding, and then at least weekly after last finding until resolution, stabilization, or return to baseline values	Hold MTX until LFTs normalize or return to baseline and consider restarting at lower dose	Hold and consider restarting after discussion with the R-Pharm International Medical Advisor or designee
>3× ULN accompanied by symptoms which, as determined by the Investigator, are the result of hepatic injury (e.g., fatigue, nausea, vomiting, right upper quadrant pain or tenderness, fever, rash, eosinophilia (>5%)	≤2× ULN	Within 72 hours of initial finding, and then at least weekly after last finding until resolution, stabilization, or return to baseline values	Hold MTX. Follow local Standard of Care.	Permanently discontinue study treatment
>3× ULN	>2× ULN	Within 72 hours of initial finding, and then at least weekly after last finding until resolution, stabilization, or return to baseline values	Hold MTX. Follow local Standard of Care.	Permanently discontinue study treatment

CL04041024: Clinical Rheumatoid Arthritis Development for Olokizumab (CREDO) 4 Olokizumab

ALT and/or AST	Total Bilirubin	Repeat Laboratory	MTX	Study Treatment
>5× ULN for for ≥2 consecutive weeks	≤2× ULN	Within 72 hours of initial finding, and then at least weekly after last finding until resolution, stabilization, or return to baseline values	Hold MTX. Follow local Standard of Care.	Permanently discontinue study treatment
>8× ULN	≤2× ULN	Within 72 hours of initial finding, and then at least weekly after last finding until resolution, stabilization, or return to baseline values	Hold MTX. Follow local Standard of Care.	Permanently discontinue study treatment

Abbreviations: ALT = alanine aminotransferase; AST = aspartate aminotransferase; MTX = methotrexate; LFTs = liver function tests; NA = not applicable; ULN = upper limit of normal.

13.2 Appendix 2: Tuberculosis Risk Questionnaire

The following questions are to be asked to every subject for evaluation of signs and symptoms of tuberculosis (TB). Responses to each question must be documented on this source document.

Question	Response
1) Does the subject have a new diagnosis of TB disease?	□ Yes □ No
2) Has the subject been in close contact (i.e., sharing the same household or other enclosed environment, such as a social gathering place, workplace, or facility, for extended periods during the day) with an individual with active TB since the last scheduled visit?	□ Yes □ No
3) Has the subject become an employee at a TB hospital, forensic medical examiner, or morgue since the last scheduled visit?	□ Yes □ No
4) Has the subject started work or has the subject stayed in long-stay institutions (e.g., homes for elderly or disabled, prisons, etc) since the last scheduled visit?	□ Yes □ No
5) Does the subject reside in or is the subject frequently travelling to a TB endemic region (as defined in Table 5)? (only applicable for subjects not living in an endemic region)	☐ Yes ☐ No ☐Not applicable
6) Has the subject been in frequent contact with underprivileged populations (homeless people or other people needing social assistance) since the last scheduled visit?	□ Yes □ No
7) Does the subject have a new cough lasting more than 14 days or a change in a chronic cough?	□ Yes □ No
8) Does the subject have night sweats?	\square Yes \square No
9) Does the subject have a persistent fever?	\square Yes \square No
10) Does the subject have unintentional weight loss (more than 10% of body weight) in the past 3 months?	□ Yes □ No
11) Does the subject appear malnourished?	\square Yes \square No
12) Has the subject had an abnormal chest X-ray since the last evaluation?	□ Yes □ No
Physician's signature:	

Table 5 List of Endemic TB Countries (Incidence >50/100,000)

Country	Incidence ^a	Country	Incidence ^a	Country	Incidence ^a
Afghanistan	189 (167–212)	Greenland	197 (173–223)	Nigeria	322 (189–488)
Algeria	78 (64–94)	Guatemala	57 (51–64)	Northern Mariana Islands	61 (53–69)
Angola	370 (240–529)	Guinea	177 (156–199)	Pakistan	270 (201–350)
Azerbaijan	77 (68–86)	Guinea-Bissau	369 (261–495)	Papua New Guinea	417 (304–547)
Bangladesh	227 (200–256)	Guyana	103 (91–116)	Peru	120 (98–145)
Belarus	58 (50–67)	Haiti	200 (177–225)	Philippines	288 (254–324)
Benin	61 (50–74)	India	167 (156–179)	Romania	81 (71–91)
Bhutan	164 (148–181)	Indonesia	399 (274–546)	Russia	84 (76–93)
Bolivia	120 (106–135)	Ivory Coast	165 (150–179)	Rwanda	63 (54–72)
Botswana	385 (361–410)	Kazakhstan	99 (64–141)	Sao Tome and Principe	97 (85–109)
Brunei	62 (54–70)	Kenya	246 (240–252)	Senegal	138 (122–154)
Burkina Faso	54 (48–59)	Kiribati	497 (406–597)	Sierra Leone	310 (235–394)
Burundi	126 (116–136)	Kyrgyzstan	142 (126–160)	Solomon Islands	86 (71–102)
Cabo Verde	138 (122–156)	Laos	189 (141–244)	Somalia	274 (242–308)
Cambodia	390 (353–428)	Lesotho	852 (612–1130)	South Africa	834 (737–936)
Cameroon	220 (195–247)	Liberia	308 (273–346)	South Korea	86 (81–91)
Central African Republic	375 (333–420)	Lithuania	62 (57–68)	South Sudan	146 (121–173)
Chad	159 (141–179)	Madagascar	235 (207–264)	Sri Lanka	65 (57–73)
China	68 (63–73)	Malawi	227 (122–365)	Sudan	94 (52–148)
China, Hong Kong	74 (65–84)	Malaysia	103 (83–124)	Swaziland	733 (533–963)
China, Macao	82 (72–93)	Mali	58 (56–59)	Tanzania	327 (155–561)
Congo	381 (335–430)	Marshall Islands	335 (274–402)	Tajikistan	91 (80–103)
Democratic Republic of	325 (295–356)	Mauritania	111 (79–148)	Thailand	171 (90–276)

R-Pharm International

 ${\rm CL04041024:}\,$ Clinical Rheumatoid Arthritis Development for Olokizumab (CREDO) 4 Olokizumab

Country	Incidencea	Country	Incidencea	Country	Incidence ^a
Congo					
Djibouti	619 (547–696)	Micronesia	195 (87–347)	Timor-Leste	498 (411–594)
Dominican Republic	60 (53–68)	Moldova	153 (135–172)	Togo	58 (47–70)
Ecuador	54 (39–71)	Mongolia	170 (149–193)	Turkmenistan	64 (52–78)
Equatorial Guinea	162 (142–184)	Morocco	106 (97–115)	Tuvalu	190 (154–228)
Eritrea	78 (57–103)	Mozambique	551 (435–680)	Uganda	161 (141–183)
Ethiopia	207 (168–250)	Myanmar	369 (334–406)	Ukraine	94 (83–106)
Fiji	67 (55–81)	Namibia	561 (492–635)	Uzbekistan	82 (61–107)
Gabon	444 (393–497)	Nauru	73 (64–83)	Vanuatu	63 (52–74)
Gambia	174 (145–206)	Nepal	158 (139–178)	Vietnam	140 (116–167)
Georgia	106 (99–114)	Nicaragua	58 (53–63)	Yemen	48 (42–54)
Ghana	165 (80–281)	Niger	98 (87–110)	Zambia	406 (279–557)
				Zimbabwe	278 (193–379)

Abbreviation: HIV = human immunodeficiency virus; TB = tuberculosis; WHO = World Health Organization.

Note: ranges represent uncertainty intervals.

Note: The 30 WHO TB high burden countries are as follows: Angola, Bangladesh, Brazil, Cambodia, China, Congo, Central African Republic, Democratic Republic of Congo, Ethiopia, India, Indonesia, Kenya, Lesotho, Liberia, Mozambique, Myanmar, Namibia, Nigeria, Pakistan, Papua New Guinea, Philippines, Russian Federation, Sierra Leone, South Africa, South Korea, Thailand, the United Republic of Tanzania, Viet Nam, Zambia, and Zimbabwe.

Source: WHO Global Tuberculosis Report 2015.

a. Rate per 100,000 population

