7.4.9 Tuberculosis Risk Questionnaire

The questionnaire "Tuberculosis Risk Questionnaire" (see Appendix 2 [Section 13.2]) should be used as a source document. The questionnaire will be completed at Visits 1 (OLE Baseline/Week 24), 4 (Week 36), 6 (Week 52), 8 (Week 76), 10 (EoT/Week 106), and SFU-2 (Week 112) as noted in Table 1.

If question No. 1 (Does the subject have a new diagnosis of active TB disease) of the TB risk questionnaire is answered with "Yes" at Visit 1 (OLE Baseline/Week 24), the subject is not allowed to enter the study (see exclusion criterion No. 2, Section 5.3.2). A "Yes" response to any of the other questions within the questionnaire at Screening should trigger further careful assessment to determine the subject's risk of TB disease.

At any visit after Visit 1 (OLE Baseline/Week 24), a "Yes" response should be treated as follows:

- Question 1: If a subject answers "Yes" study treatment should be discontinued if active TB is confirmed (see Section 6.11).
- Questions 2 through 6: If a subject answers "Yes" to any question, they should be assessed (TB risk questionnaire and physical examination) 12 weeks from the time of exposure to determine if the subject developed TB. The Investigator should consult with a certified TB specialist or pulmonologist, if needed.
 - Questions 7 through 12: If a subject answers "Yes" to any question, this should trigger a careful assessment to determine if the subject developed TB (see Section 7.4.10).

This risk questionnaire is not to be used to exclude TB disease or confirm diagnosis.

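### Four exposure questions on the TB risk questionnaire look back only to the last scheduled visit, so read literally 38 of 88 nominal weeks (43%) fall in no question's recall window

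*Combined protocol and SAP*

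**What the plan says.** Appendix 2 (Section 13.2) has five questions on exposure. Four share one look-back anchor:

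- Question 2, close contact: "with an individual with active TB since the last scheduled visit"
- Question 3, employment: "Has the subject become an employee at a TB hospital, forensic medical examiner, or morgue since the last scheduled visit"
- Question 4, work or stay in long-stay institutions: "e.g., homes for elderly or disabled, prisons, etc) since the last scheduled visit"
- Question 6, contact with underprivileged groups: "homeless people or other people needing social assistance) since the last scheduled visit"

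Question 5 has no look-back: "Does the subject reside in or is the subject frequently travelling to a TB endemic region". Question 12 uses a different anchor: "Has the subject had an abnormal chest X-ray since the last evaluation".

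Section 7.4.9 places the form at Visit 1 (Week 24) and then at Visits "4 (Week 36), 6 (Week 52), 8 (Week 76), 10 (EoT/Week 106), and SFU-2 (Week 112) as noted in Table 1". Table 1 agrees. The visit lists in Sections 5.4.1 and 5.4.3 omit it at Visits 2, 3, 5, 7 and 9 and at SFU-1 and SFU-3.

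After Visit 1, Section 7.4.9 responds to a Yes on any of Questions 2 to 6 with a reassessment, consisting of the questionnaire and a physical examination, timed at 12 weeks after the exposure.

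**The concern.** The recall window and the administration schedule do not fit together. The window reaches back one visit, while the form is given at most every second visit. A subject who had household contact with a TB case from Week 53 to Week 60 can truthfully answer No at Week 76, because the last scheduled visit was Week 64. No earlier form covered that contact either.

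What is lost is the investigator's knowledge of the exposure, and with it the trigger for the Section 7.4.9 assessment. TB is an adverse event of special interest (Section 7.4.3), and confirmed active TB is reported as an SAE. The study enrols in Russia and Belarus, both listed as endemic in Table 5. Question 5 is marked as applying only to subjects who do not live in an endemic region, so for residents of those countries the four affected questions are all the exposure questions that apply.

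**Working it through.** The documents give no coverage figure to reproduce. The check is interval arithmetic on nominal visit weeks.

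**Inputs.** Scheduled visits (Table 1): Weeks 24, 26, 28, 36, 44, 52, 64, 76, 88, 106, 108, 112, 126. Questionnaire visits (Section 7.4.9, Table 1): Weeks 24, 36, 52, 76, 106, 112.

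**Formulas.** For each form after Week 24:

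- covered = week of this form − week of the scheduled visit just before it
- missed = week of that preceding visit − week of the previous form

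| Form at week | Preceding scheduled visit | Previous form | Covered (weeks) | Missed (weeks) |
|---|---|---|---|---|
| 36 | 28 | 24 | 36 − 28 = 8 | 28 − 24 = 4 |
| 52 | 44 | 36 | 52 − 44 = 8 | 44 − 36 = 8 |
| 76 | 64 | 52 | 76 − 64 = 12 | 64 − 52 = 12 |
| 106 | 88 | 76 | 106 − 88 = 18 | 88 − 76 = 12 |
| 112 | 108 | 106 | 112 − 108 = 4 | 108 − 106 = 2 |
| Total | | | 50 | 38 |

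**Results.**

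- Weeks 24 to 112: 38 / (50 + 38) = 38/88 = 43.2%.
- Treatment period, Weeks 24 to 106: (4 + 8 + 12 + 12)/82 = 36/82 = 43.9%.
- Weeks 112 to 126 (14 weeks) have no later form at all. Counting them gives (38 + 14)/102 = 52/102 = 51.0%. This part comes from the schedule, not from the wording, and is left out of the 43%.

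**How much of the 12-week assessment is at stake.** The triggered assessment is the same form plus an examination, so it matters whether the next form already falls at least 12 weeks after the exposure:

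- Exposure in Weeks 36-40, next form Week 52: yes, 4 weeks.
- Exposure in Weeks 52-64, next form Week 76: yes, 12 weeks.
- Exposure in Weeks 76-88, next form Week 106: yes, 12 weeks.
- Exposure in Weeks 24-28, 40-44 or 106-108: no, 4 + 4 + 2 = 10 weeks.

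So for 4 + 12 + 12 = 28 of the 38 weeks (28/38 = 74%), the symptom questions and an examination already take place 12 weeks or more after exposure, although without knowledge of it. For the other 10 weeks a 12-week assessment that still lay ahead is not set up.

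**After the rewording.** Recall windows become 12, 16, 24, 30 and 6 weeks, which sum to 88. Missed weeks between Weeks 24 and 112 fall from 38 to 0.

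**The case against.** The strongest reply is that a site could take the last scheduled visit to mean the last visit at which this form was completed, which leaves no gap. That is possible, but nothing in the documents says it. Section 5.5 and the footnotes to Table 1 call Visits 2 through 9 scheduled visits, and Question 12 on the same form uses another anchor. That other anchor is itself undefined and could mean the last X-ray evaluation. At best the form is ambiguous and sites may apply different windows.

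Several limits on the harm do stand:

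- Contact or a stay that continues past the intervening visit is mostly still captured. The loss concerns exposures that ended inside a gap and jobs that started there.
- Other safeguards remain: symptom Questions 7 to 11, examinations with a respiratory component at every visit, adverse event questioning, chest X-rays at Weeks 24, 52 and 106, and IGRA at Weeks 52 and 106 for previously negative subjects. They are partial. None asks about exposure, adverse event questioning is non-directive (Section 7.4.1.1), and Section 7.4.3.1 warns that signs of acute inflammation may be muted.
- Section 7.4.9 says that the form neither excludes nor confirms TB, and no endpoint or planned analysis uses the answers.

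A reader might go further and infer that dosing continues because of the wording, or that a Week 53 contact waits until Week 106 (53 weeks) for an IGRA because of it. The documents support neither inference. Under Section 7.4.9 a Yes to Questions 2 to 6 leads to an assessment, with no dosing hold and no IGRA. The IGRA interval is the same under either wording.

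**Conclusion.** The point holds as a mismatch between the form's wording and its schedule. Followed as written, Questions 2, 3, 4 and 6 leave 38 of 88 nominal weeks (43%), or 36 of 82 on treatment (44%), in no recall window. An exposure confined to those weeks yields a truthful No, and the Section 7.4.9 assessment is not triggered.

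The consequence is lost exposure history and a missed trigger. It is not a change in treatment, and it does not bias any planned estimate. For 28 of the 38 weeks the main loss is the investigator's knowledge of the exposure; for about 10 weeks it is also a 12-week assessment that still lay ahead.

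The figures assume the literal reading, nominal visit weeks and subjects who stay on treatment to Week 104. Visit windows of ±5 or ±7 days, and early discontinuation (which moves Visit 10), change individual values. The look-back of the Week 24 form is not counted, because the core-study visit schedules are not in these documents.

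**What to change.** In Appendix 2, Questions 2, 3, 4 and 6, replace the look-back phrase with *since this questionnaire was last completed*. For Visit 1, add *since the last TB questionnaire in the core study, if any*; the qualifier is needed because these documents do not show whether the core studies used such a form. Leave the visits, tests and clinical rules as they are.

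The cost is one phrase in four questions on one source form. The downside is longer recall: the longest window rises from 18 weeks (88 to 106) to 30 weeks (76 to 106). The rewording does not make reporting prompt. A contact at Week 53 would first be asked about at Week 76, 23 weeks later and after the 12-week point, but it would be asked about. Weeks 112 to 126 would still have no form.
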